### 9.2.2 Sensitivity Analyses

Besides stratification by age the randomisation is also stratified by trial site. However, as detailed above, the primary analysis will be based on all data pooled across sites assuming homogeneity of the risk differences across sites. This assumption will be tested using the approach described by Lipsitz et al. (1998). Sites where all subjects have a positive outcome and sites where all subjects have a negative outcome will be excluded from this analysis. In addition sites with at most one subject in any treatment group will be excluded from this sensitivity analysis. If there is statistically significant heterogeneity across sites the implications for the interpretation of the primary result will be discussed.

To evaluate the robustness of the conclusions, the following factors potentially impacting ongoing pregnancy will be evaluated one by one:

- Insemination method
- Primary reason for infertility
- Primary infertility
- Smoking status

For each factor, the primary analysis will be repeated using the factor levels as strata instead of the age stratification. The outcomes of these analyses are considered supportive and should lead to similar results as the primary analysis to ensure robustness of the conclusion.

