### **Additional Analyses, including Sensitivity Analysis**

The primary analyses described above will be repeated restricted to subjects with oocytes retrieved and to subjects with embryo(s) transferred. Since the trial is not powered to establish non-inferiority for these subgroups, the outcomes of these analyses are considered supportive of the primary analysis.

Besides stratification by age group the randomisation is also stratified by trial site. However, as detailed above, the primary analysis will be based on all data pooled across sites assuming homogeneity of the risk differences across sites. This assumption will be tested using the approach described by Lipsitz et al. (1998). If there is statistically significant heterogeneity across sites the implications for the interpretation of the primary result will be discussed.

To evaluate the robustness of the conclusions, the following factors potentially impacting ongoing pregnancy will be evaluated one by one:

- Insemination method
- Primary reason for infertility
- Primary infertility
- Smoking status

For each factor, subjects will be grouped according to the levels of the factor and the primary analysis will be repeated using this grouping. The outcomes of these analyses are considered supportive and should lead to similar results as the primary analysis to ensure robustness of the conclusion.

As described in Section 6.5.1, transfer of one or two embryo(s) is to be performed on day 3 after oocyte retrieval. The decision to transfer either one or two embryo(s) is based on the subject's age and the quality and availability of embryo(s) on the day of transfer. Since this decision is based on observations performed after randomisation it can be affected by the treatment allocation. It is therefore not planned to perform a formal statistical analysis of the ongoing pregnancy rate adjusting for number of embryos transferred. The rationale for not including these adjustments in the primary analysis is that such an adjustment may hide or exaggerate the differences between treatments. Instead the ongoing pregnancy rate will be presented by number of embryos transferred. Further, a frequency table will be produced to compare the treatment groups with respect to number of embryos transferred.

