### 6.2 Full Analysis Set

The FAS is defined as all randomised and exposed subjects. Subjects will be analysed according to randomised (planned) treatment.

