## 6.5 Subgroups

Data will in some cases be reported using the following subgroups:

- Subjects grouped according to AMH at screening ( $<15$  pmol/L,  $\geq 15$  pmol/L)
- Subjects with at least 1 oocyte retrieved
- Subjects with transfer
- Subjects grouped according to number of embryos transferred (single, double)
- Subjects grouped according to ongoing pregnancy type (single, twin, triplet)
- Subjects grouped according to insemination method
- Subjects grouped according to primary reason for infertility
- Subjects grouped according to primary infertility
- Subjects grouped according to smoking status

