### 9.2.3 Supplementary Descriptions

The ongoing pregnancy rate will be summarised for subjects with at least one oocyte retrieved and for subjects with transfer. The purpose of this is purely descriptive.

As described in the protocol Section 6.5.1, transfer of one or two embryo(s) is to be performed on day 3 after oocyte retrieval. The decision to transfer either one or two embryo(s) is based on the subject's age and the quality and availability of embryo(s) on the day of transfer. Since this decision is based on observations performed after randomisation it can be affected by the treatment allocation. It is therefore not planned to perform a formal statistical analysis of the ongoing pregnancy rate adjusting for number of embryos transferred. The rationale for not including these adjustments in the primary analysis is that such an adjustment may hide or exaggerate the differences between treatments. Instead the ongoing pregnancy rate will be presented by number of embryos transferred. Further, a frequency table will be produced to compare treatments with respect to number of embryos transferred.

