## **Implantation Rate**

Implantation rate is defined as the number of gestational sacs 5-6 weeks after transfer divided by number of embryos transferred. For implantation rate, the experimental unit will be the transferred embryos, i.e., the analysis will compare the proportions of embryos transferred that results in gestational sacs 5-6 weeks after transfer. The implantation rate will be analysed in a similar manner as the primary endpoint. Note that this endpoint is less relevant than the pregnancy endpoints since it is only defined in the subgroup of subjects that had an embryo transfer, and hence does not adhere to the randomisation principle.

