## **Fertilisation Rate**

An oocyte is defined as fertilised if it is scored as 2 pronuclei on day 1 after oocyte retrieval. For subjects with oocytes retrieved, the rate of fertilised oocytes to oocytes retrieved (and also the rate of fertilised oocytes to metaphase II oocytes for those inseminated using ICSI) will be tabulated. The number of fertilised oocytes and the fertilisation rate will be compared between treatment groups using the van Elteren test stratified for age and within each age stratum using the Wilcoxon's test. Subjects will be grouped according to number of fertilised oocytes as: <4, 4-7, 8-14, 15-19,  $\geq 20$  and the corresponding frequencies tabulated. Note that the analysis of fertilisation rates excludes subjects without oocytes retrieved and do therefore not adhere to the randomisation principle.

## Number and Quality of Embryos on Day 3

Based on the embryo assessment day 3 the following endpoints are defined:

- Number of embryos
- Number of good-quality embryos
- Subjects with at least one embryo
- Subjects with at least one good-quality embryo
- Rate of embryos to oocytes retrieved
- Rate of good-quality embryos to oocytes retrieved
- Rate of embryos to MII oocytes
- Rate of good-quality embryos to MII oocytes
- Number of cryopreserved embryos
- Subjects with at least one cryopreserved embryo

Numbers and rates will be compared between treatments using the van Elteren test stratified for age and within each age stratum using the Wilcoxon's test. For each definition of 'subjects with at least one' the proportion of subjects will be tabulated and analysed in a similar manner as extreme ovarian response.

Embryo quality will be summarised including a breakdown by selected quality parameters (degree of fragmentation, embryo stage, blastomere uniformity, visual sign of multi-nucleation) and insemination method. Separate summaries will be made for the transferred embryos and for the cryopreserved embryos.

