## 12 Changes Compared to the Analyses Described in the Trial Protocol

There are no changes to the primary analysis planned in the protocol for the primary endpoint. The sensitivity analyses planned on subgroups of subjects (subjects with oocytes retrieved and subjects with transfer) have been excluded since these analyses do not adhere to the randomisation principle. Descriptive statistics will be used to present the results in the subgroups.

For the secondary endpoints, details and context of the analyses described in the protocol have been clarified and some additional analyses have been included to make the result description more complete. The proposed analyses for ordinal data have been excluded since there are no ordinal endpoints. For example a grouping based on increasing number of oocytes retrieved is ordinal, however, the corresponding ovarian response (low response, moderate response, target response, hyperresponse, severe hyperresponse) is not ordinal. The treatment comparisons will be carried out as planned based on the ungrouped data.

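### Insemination method is used as a stratification factor in SAP 9.2.2, although it is observed after randomisation and has no value for women who never reach insemination

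*SAP*

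**What the plan says.** SAP 9.2.2 (Sensitivity Analyses) names insemination method, primary reason for infertility, primary infertility and smoking status, and then states: "For each factor, the primary analysis will be repeated using the factor levels as strata instead of the age stratification". It expects the results to agree with the primary analysis, as support for robustness. Protocol 9.7.2 plans the same: "For each factor, subjects will be grouped according to the levels of the factor and the primary analysis will be repeated using this grouping".

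SAP 6.5 only names the grouping ("Subjects grouped according to insemination method"). It gives no levels. The analysis population is wider than the women who have a method: "The FAS is defined as all randomised and exposed subjects" (SAP 6.2).

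Elsewhere the SAP is cautious about factors that arise after randomisation:

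- **SAP 9.2.3** declines to adjust for number of embryos transferred: "Since this decision is based on observations performed after randomisation it can be affected by the treatment allocation".
- **SAP 12** says that the protocol's analyses in women with oocytes retrieved and in women with transfer "have been excluded since these analyses do not adhere to the randomisation principle".
- **SAP 9.3, implantation rate**, keeps a formal analysis but warns that "it is only defined in the subgroup of subjects that had an embryo transfer, and hence does not adhere to the randomisation principle".
- **SAP 9.3, fertilisation rate**, does likewise: "Note that the analysis of fertilisation rates excludes subjects without oocytes retrieved and do therefore not adhere to the randomisation principle".

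SAP 9.2.2 carries no such warning for insemination method.

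**The concern.** Randomisation is on cycle day 2-3 (Protocol 4.2.2). Insemination takes place on the day of retrieval (Protocol 6.4), after stimulation and triggering. A woman whose cycle is cancelled (Protocol 6.2.4) or who has no oocytes (Protocol 6.3) has no insemination method, yet she stays in the FAS and counts as not pregnant (SAP 9.1, Missing Data). Some women may have both methods, because the metaphase II section of SAP 9.3 singles out those whose oocytes all had ICSI. Neither document says how either group enters the strata, and neither defines a planned method recorded before randomisation.

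Treatment can affect who reaches insemination. Protocol 3.5.4 reports that this dosing regimen reduced cancellation for excessive response in ESTHER-1. If the arms differ in non-insemination, stratifying by observed method takes that part of the treatment effect out of the estimate. Agreement with the primary result would then say nothing about this route, and disagreement could be an artefact of the conditioning. What is at stake is how one supportive table is read.

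No bias is claimed from the choice between IVF and ICSI itself.

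**Working it through.** **Background figure.** The point rests on no planned figure, but the sample size reproduces. With a 32.2% rate in both arms, a 10-point margin, one-sided 0.025 and 90% power, n per arm = 2 × 0.322 × 0.678 × (1.960 + 1.282)² / 0.10² = 459, or 918 in total, as stated. Nothing below changes it.

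**Inputs.**

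- From the documents: the Mantel-Haenszel risk difference and standard error in SAP 9.2.1, the 32.2% rate, and 1,000 women, hence 500 per arm.
- Assumed, because the documents give no non-insemination rate: proportions not inseminated qF (FE 999049) and qG (GONAL-F), a rate among inseminated women of p = 0.322/0.95 = 0.339, and a 60/40 IVF/ICSI split. Age strata are left out of the FAS comparison for simplicity.

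**Formulas when p is equal in both arms.**

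- FAS difference = p(1 − qF) − p(1 − qG) = p(qG − qF).
- Women without a method dropped: each stratum compares p with p, so the estimate is 0.
- Separate 'none' stratum: both arms have zero events, so its risk difference is 0 and the combined estimate is again 0.

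In numbers, 0.339 × (0.05 − 0.02) = +1.02 points and 0.339 × (0.05 − 0.10) = −1.69 points.

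**Results: difference in points (95% CI).**

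| FE deficit among inseminated | qF vs qG | FAS | Dropped | 'None' stratum |
|---|---|---|---|---|
| 0 | 2% vs 5% | +1.02 (−4.80 to 6.83) | 0.00 (−5.97 to 5.97) | 0.00 (−5.80 to 5.80) |
| 0 | 10% vs 5% | −1.69 (−7.44 to 4.06) | 0.00 (−6.10 to 6.10) | 0.00 (−5.69 to 5.69) |
| 3 points | 2% vs 5% | −1.92 (−7.67 to 3.82) | −3.00 (−8.90 to 2.90) | −2.91 (−8.65 to 2.82) |
| 3 points | 10% vs 5% | −4.39 (−10.07 to 1.28) | −3.00 (−9.03 to 3.03) | −2.80 (−8.42 to 2.83) |

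In the last row the FAS lower limit misses the −10.0 margin while both versions of the check clear it. In the third row the check is too pessimistic.

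**Range.** For p from 30% to 50%, a 3-point gap in non-insemination hides 0.03 × 0.30 = 0.9 to 0.03 × 0.50 = 1.5 points. A 5-point gap hides 1.5 to 2.5 points.

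**Reverse case.** Suppose the FAS rates are equal at 32.2%, so the true FAS difference is 0, with an equal IVF/ICSI split. With 3% vs 8% not inseminated, the estimate is −1.8 points (dropped) or −1.7 ('none' stratum). Dropping with 8% vs 3% gives +1.8.

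**Source of the loss.** Strata by a hypothetical planned method, defined for every woman, return the FAS results exactly (+1.02 and −1.69). The loss therefore comes from using the observed method and not from stratifying.

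**Upper bound.** To produce a 10-point deficit by this route alone, the excess in non-insemination would have to be 0.10/0.339 = 29.5 points.

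**The case against.** **Part of the excessive-response route is kept.** Women with 25-35 follicles can receive a GnRH agonist instead of cancellation (Protocol 6.2.4). Their oocytes are retrieved and go through the section 6.4 procedures, so they have a method; they have no fresh transfer and count as negative. If 2% vs 5% were such cycles and every woman was inseminated, the FAS and stratified estimates would be identical at +1.02. With an assumed 1.5% vs 4% agonist cycles and 0.5% vs 1% not inseminated, the FAS difference is +1.02 against +0.86 (dropped) or +0.85 ('none' stratum). This stands: the real gap may be much smaller than the table's.

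**The margin-crossing row is contrived.** It needs more non-insemination with FE 999049, opposite to the ESTHER-1 finding on excessive-response cancellation, plus a 3-point deficit. In that row the FAS analysis fails anyway, so no claim would be made. This stands too.

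**There may be no true contradiction.** Number of embryos depends on embryo quality and availability, and the documents state no such basis for choosing IVF or ICSI. SAP 9.2.2 also announces no restriction to a subset. This holds for the choice of method, but not for women with no method. Dropping them leaves essentially the oocytes-retrieved subset that section 12 removed.

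**Defining levels and adding a caveat would be enough.** The table shells are in a separate document and could set the levels, and the implantation and fertilisation analyses keep formal tests with a warning. Defined levels would settle the programming. They would not repair the estimate, because a 'none' level also returns 0.00. A caveat would be a weaker remedy.

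**Conclusion.** The concern holds and is minor. The factor is observed after randomisation, it is undefined for part of the FAS, and neither obvious handling keeps a treatment difference that arises before insemination. This goes beyond a missing definition, because the analysis cannot support robustness for that route.

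The size is modest: about 1 to 2.5 points for gaps of 3 to 5 points in non-insemination, with the sign following the direction of the gap, and nothing if the arms do not differ. These gaps are assumptions, and agonist-triggered cycles would make them smaller. The non-inferiority decision rests on the age-stratified FAS and per-protocol analyses and is unchanged. The route also remains visible in the FAS result itself, in the completion summaries (SAP 4), and in the ovarian-response and cancellation comparisons (SAP 9.3).

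**What to change.** - **SAP 9.2.2:** remove insemination method from the stratified analyses. Keep primary reason for infertility, primary infertility and smoking status, which are collected at screening (Protocol 7.3.3, 7.3.5 and 7.3.6).
- **SAP 9.2.3:** present the ongoing pregnancy rate by insemination method descriptively, as for number of embryos transferred, with not inseminated and mixed IVF/ICSI as separate categories.
- **SAP 12:** record the departure from Protocol 9.7.2 beside the two subset analyses already removed, for the same reason.

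The cost is a few lines of SAP text. One supportive table planned in the protocol loses its confidence interval.

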### 9.2.3 Supplementary Descriptions

The ongoing pregnancy rate will be summarised for subjects with at least one oocyte retrieved and for subjects with transfer. The purpose of this is purely descriptive.

As described in the protocol Section 6.5.1, transfer of one or two embryo(s) is to be performed on day 3 after oocyte retrieval. The decision to transfer either one or two embryo(s) is based on the subject's age and the quality and availability of embryo(s) on the day of transfer. Since this decision is based on observations performed after randomisation it can be affected by the treatment allocation. It is therefore not planned to perform a formal statistical analysis of the ongoing pregnancy rate adjusting for number of embryos transferred. The rationale for not including these adjustments in the primary analysis is that such an adjustment may hide or exaggerate the differences between treatments. Instead the ongoing pregnancy rate will be presented by number of embryos transferred. Further, a frequency table will be produced to compare treatments with respect to number of embryos transferred.

## 9.3 Secondary Endpoints

For each secondary endpoint the analysis based on the FAS will be used to assess the statistical significance of differences between treatments. The analysis based on the PP analysis set will be considered supportive and should lead to a similar but not necessarily statistically significant result in order to have a robust interpretation.

Statistical tests will be performed using a two-sided test at a 5% significance level. Treatment differences will (where appropriate) be presented with 95% confidence intervals and p-values corresponding to the statistical test of the hypothesis of 'equal effect' against the alternative of 'different effect'.

### Positive $\beta$ hCG Rate

Positive  $\beta$ hCG is defined as positive serum  $\beta$ hCG test 13-15 days after transfer. The positive  $\beta$ hCG rate is considered supportive to the primary endpoint and will therefore be analysed in a similar manner as the primary endpoint.

## **Clinical Pregnancy Rate**

Clinical pregnancy is defined as at least one gestational sac 5-6 weeks after transfer. The clinical pregnancy rate is considered supportive to the primary endpoint and will therefore be analysed in a similar manner as the primary endpoint. For subjects with clinical pregnancy, the type of clinical pregnancy (intrauterine or ectopic) will be tabulated.

## **Vital Pregnancy Rate**

Vital pregnancy is defined as at least one intrauterine gestational sac with fetal heart beat 5-6 weeks after transfer. The vital pregnancy rate is considered supportive to the primary endpoint and will therefore be analysed in a similar manner as the primary endpoint. For subjects with a vital pregnancy, the number of intrauterine gestational sacs with fetal heart beat and the number of fetuses with fetal heart beat will be tabulated.

## **Implantation Rate**

Implantation rate is defined as the number of gestational sacs 5-6 weeks after transfer divided by number of embryos transferred. For implantation rate, the experimental unit will be the transferred embryos, i.e., the analysis will compare the proportions of embryos transferred that results in gestational sacs 5-6 weeks after transfer. The implantation rate will be analysed in a similar manner as the primary endpoint. Note that this endpoint is less relevant than the pregnancy endpoints since it is only defined in the subgroup of subjects that had an embryo transfer, and hence does not adhere to the randomisation principle.

## **Ongoing Implantation Rate**

Ongoing implantation rate is defined as the number of intrauterine viable fetuses 10-11 weeks after transfer divided by number of embryos transferred. For ongoing implantation rate, the experimental unit will be the transferred embryos, i.e., the analysis will compare the proportions of embryos transferred that results in intrauterine viable fetuses 10-11 weeks after transfer. The ongoing implantation rate will be analysed in a similar manner as the primary endpoint.

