During stimulation, subjects will be monitored by transvaginal ultrasound on stimulation day 1 and 6 and hereafter at least every second day. When the leading follicle reaches ≥15 mm, visits must be performed daily. To prevent a premature LH surge, a GnRH antagonist will be initiated on stimulation day 6 and continued throughout the stimulation period. Triggering of final follicular maturation will be done as soon as ≥3 follicles with a diameter ≥17 mm are observed. If there are <25 follicles with a diameter ≥12 mm, hCG will be administered. If there are 25-35 follicles with a diameter ≥12 mm, a GnRH agonist can be administered or the cycle can be cancelled. In case of excessive follicular development, defined as >35 follicles with a diameter ≥12 mm, the cycle is to be cancelled. If it is judged by the investigator that ≥3 follicles with a diameter ≥17 mm cannot be reached, but 1 or 2 follicles with a diameter ≥17 mm are observed, the cycle may either be cancelled due to poor follicular development or triggering of final follicular maturation is to be induced, as judged by the investigator.

Oocyte retrieval will take place 36h ( $\pm$ 2h) after triggering of final follicular maturation and the oocytes can be inseminated by IVF or ICSI. Rescue ICSI is not allowed. Fertilisation and embryo development will be assessed from oocyte retrieval to the day of transfer. For subjects who underwent triggering of final follicular maturation with hCG, transfer is performed on day 3 (embryo stage) after oocyte retrieval. Subjects <35 years at randomisation will have single embryo transfer if a good-quality embryo is available; otherwise, double embryo transfer will be performed (and single transfer if two embryos are not available). Subjects  $\geq$ 35 years at randomisation will have double embryo transfer (and single transfer if two embryos are not available). Remaining embryos may be cryopreserved in accordance with local guidelines and/or regulations. For subjects who underwent triggering of final follicular maturation with GnRH agonist, no transfer will take place in the current fresh cycle and the embryos available will be cryopreserved on day 3, 5 or 6, according to local practice. All cryopreserved embryos can be used by the subject after completion of the trial, in accordance with local guidelines and/or regulations.

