## 6.5 Transfer

### 6.5.1 Embryo Transfer

Transfer is performed on day 3 (embryo stage) after oocyte retrieval. The subject-related procedures are described below.

- Blood collection for central laboratory analysis of anti-FSH antibodies (first post-dosing assessment)
- Transfer of 1 or 2 embryo(s) of the highest quality available according to this policy:
  - Subjects <35 years at randomisation:
    - single embryo transfer if a good quality embryo is available
    - double embryo transfer if a good-quality embryo is not available (and single transfer if two embryos are not available).
  - Subjects  $\geq 35$  years at randomisation:
    - double embryo transfer (and single transfer if two embryos are not available).

(note: transfer is only applicable for subjects who underwent triggering of final follicular maturation with hCG. Subjects who were administered GnRH agonist will not undergo transfer in the current fresh cycle).

- Dispensing of progesterone for luteal phase support
- Drug accountability of progesterone
- Recording of use of any concomitant medication
- Recording of adverse events

For subjects with embryo transfer, the next visit is the  $\beta$ hCG test visit which must be scheduled 13-15 days after transfer (section 6.6).

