# **9 Efficacy**

## **9.1 General Considerations**

### **Primary and Secondary Endpoints**

The results of the analyses of the primary endpoint (ongoing pregnancy rate) based on the overall Pan-Asian trial population are essential for the non-inferiority claim. The results obtained for the Chinese trial population is considered supportive of the overall conclusion. If the results for the Chinese trial population are markedly different from those obtained based on the overall Pan-Asian trial population the reasons for this difference will be examined. The secondary endpoints positive  $\beta\text{hCG}$  rate, clinical pregnancy rate, vital pregnancy rate, implantation rate and ongoing implantation rate are considered supportive of the primary endpoint. However, non-inferiority does not need to be established for these secondary endpoints.

The remaining secondary endpoints are intended to provide additional characterisation of the safety and efficacy of FE 999049.

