There is no need for a multiplicity adjustment when switching from non-inferiority to superiority since it is a simple sequential test procedure. This interpretation is in line with the Food and Drug Administration (FDA) draft guidance on “Multiplicity” and EMA’s “Points to consider on switching between superiority and non-inferiority”.

The two-sided 95% confidence intervals will be constructed based on the asymptotic normal distribution as

$$\frac{\sum w_i RD_i}{\sum w_i} \pm 1.96 \sqrt{\frac{\sum w_i^2 SE(RD_i)^2}{(\sum w_i)^2}},$$

where the sums are over the three age strata (i.e.  $i = 1$  to  $3$ ),  $RD_i = \hat{\pi}_{FE,i} - \hat{\pi}_{GF,i}$  is the observed difference in rates (FE 999049 - GONAL-F) within stratum  $i$ ,

$SE(RD_i) = \sqrt{\frac{\hat{\pi}_{FE,i}(1-\hat{\pi}_{FE,i})}{n_{FE,i}} + \frac{\hat{\pi}_{GF,i}(1-\hat{\pi}_{GF,i})}{n_{GF,i}}}$  is the standard error of the observed difference in rates within stratum  $i$ ,

$w_i = \frac{n_{FE,i} n_{GF,i}}{n_{FE,i} + n_{GF,i}}$  is the weight assigned to stratum  $i$ ,

$\hat{\pi}_{FE,i}, \hat{\pi}_{GF,i}$  are the observed rates for each treatment group and stratum, and

$n_{FE,i}, n_{GF,i}$  are the number of observations in each treatment group and stratum.

A supportive evaluation of the subjects recruited in China will be made and it is expected that the findings among the Chinese trial population will be consistent with the overall findings in the trial. If the results based on the Chinese trial population are markedly different from those obtained based on the overall Pan-Asian trial population the reasons for this difference will be examined.

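### The implantation-rate analyses count two embryos from one woman as independent, so their confidence intervals are too narrow if outcomes within a woman are positively correlated

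*SAP*

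**What the plan says.** For ongoing implantation rate, SAP 9.3 states: "For ongoing implantation rate, the experimental unit will be the transferred embryos". It makes the embryo the unit for implantation rate too, as does protocol 9.7.3 for both endpoints. The SAP adds the method: "The implantation rate will be analysed in a similar manner as the primary endpoint", and it says the same of ongoing implantation rate.

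That method, in SAP 9.2.1, is a risk difference combined over three age strata with Mantel-Haenszel weights and a normal-approximation 95% confidence interval. The variance is p(1−p)/n for each arm and stratum, where the n's "are the number of observations in each treatment group and stratum".

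The number of embryos per woman varies. Protocol 3.1.2 says: "Subjects <35 years at randomisation will have single embryo transfer if a good-quality embryo is available; otherwise, double embryo transfer will be performed". For women aged 35 and over, protocol 6.5.1 prescribes "double embryo transfer (and single transfer if two embryos are not available").

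On the use of the results, SAP 9.3 says: "Treatment differences will (where appropriate) be presented with 95% confidence intervals and p-values". SAP 9.1 names both implantation endpoints as supportive of the primary, with this limit: "However, non-inferiority does not need to be established for these secondary endpoints". For implantation rate the SAP also warns: "Note that this endpoint is less relevant than the pregnancy endpoints". Its reason is that the endpoint exists only for women who had a transfer.

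**The concern.** The binomial variance is right when each observation is independent. For the primary endpoint it is: one woman gives one outcome. Once n counts embryos, a woman with a double transfer enters twice, and nothing in either document allows for her two outcomes being related.

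A positive relation is plausible. The two embryos share one uterus, one stimulation cycle and one course of luteal support. The missing-data rule in SAP 9.1 adds a little: a woman with a transfer but no fetus count is set to zero viable fetuses, so both her embryos fail together. That effect is small if missing data are rare.

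The SAP's own practice differs elsewhere. Fertilisation and embryo rates are compared with van Elteren and Wilcoxon tests on one value per woman, and follicle-level counts are only summarised. The implantation endpoints appear to be the only treatment comparisons with a unit below the woman.

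At stake is the honesty of the intervals and p-values for two endpoints presented as support for the primary result, in the overall and the Chinese populations. Ongoing implantation rate was co-primary in ESTHER-1, so it will be read closely.

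**Working it through.** **1. The plan's own figure.** The planned rate is 32.2% in both arms, the margin 10 points and the power 90% (protocol 9.1, SAP 3.2). With independent-binomial variance:

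n per arm = (1.960 + 1.282)² × 2 × 0.322 × 0.678 / 0.10² = 10.507 × 0.4366 / 0.01 = 458.8, so 459 per arm and 918 in total, as stated.

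The standard error is √(0.4366/459) = 0.0308, the 3.1% in protocol Table 9-1. The plan's variance is therefore the independent-binomial one. That is correct for women.

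**2. What changes when n counts embryos.** Let f be the share of women with a transfer who receive two embryos, and ρ the correlation between two embryos in one woman. For N women in one arm and stratum there are N(1+f) embryos. The variance of the number of successes is

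p(1−p) × [N(1−f) + Nf(2+2ρ)] = p(1−p) × N(1+f+2fρ).

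Dividing by [N(1+f)]², and comparing with the planned p(1−p)/[N(1+f)], gives

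variance inflation = 1 + 2fρ/(1+f).

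This cannot exceed 1+ρ (reached at f = 1), and it equals 1 at ρ = 0.

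**3. Size in closed form.** The documents give neither f nor ρ, so both are assumed. The true level of a nominal 5% test is 2[1 − Φ(1.96/√inflation)].

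| f | ρ | Inflation | Planned SE too small by | True level |
|---|---|---|---|---|
| 0.3 | 0.1 | 1 + 0.06/1.3 = 1.046 | 2.2% | 5.5% |
| 0.5 | 0.3 | 1 + 0.30/1.5 = 1.200 | 8.7% | 7.4% |
| 0.7 | 0.5 | 1 + 0.70/1.7 = 1.412 | 15.8% | 9.9% |

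**4. The age-stratified formula.** Assume:
- 400 women with a transfer per arm, split 70/17/13% by age stratum
- double transfer in 10/90/90% (overall f = 0.34)
- per-embryo rates of 36/30/20%
- ρ = 0.3

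Embryos per arm are 280 × 1.1 = 308, 68 × 1.9 = 129.2 and 52 × 1.9 = 98.8, in total 536.

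- Planned variance: 2 × (308×0.2304 + 129.2×0.21 + 98.8×0.16)/536² = 2 × 113.9/287,296, so SE 0.0282 and half-width 5.5 points.
- Inflation per stratum: 1 + 0.06/1.1 = 1.055 under 35, and 1 + 0.54/1.9 = 1.284 in each older stratum.
- Corrected variance: 2 × 130.0/287,296, so SE 0.0301 and half-width 5.9 points.
- The true SE is 1.068 times the planned one and the true level is 6.7%. A simulation with 40,000 replicates gave 6.8%, and 5.1% at ρ = 0.

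With 50–80% of women under 35, double transfer in 10–30% of them and in 90–95% of older women, and ρ from 0.1 to 0.5, the true SE is 1.02 to 1.17 times the planned one and the level 5.4% to 9.4%.

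**5. Simulation of the SAP 9.2.1 formula.** No treatment effect, 400 transfers per arm, per-embryo rates 35/28/22%, 10,000 replicates per cell. Rejection rate with the planned SE:

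| Age split; double-transfer shares (overall f) | ρ=0 | 0.1 | 0.2 | 0.3 | 0.5 |
|---|---|---|---|---|---|
| 75/15/10%; 10/85/85% (0.29) | 4.7% | 5.6% | 6.2% | 6.8% | 7.0% |
| 65/20/15%; 20/90/90% (0.45) | 4.8% | 5.6% | 6.4% | 7.1% | 8.4% |
| 50/25/25%; 40/95/95% (0.68) | 5.2% | 6.0% | 6.5% | 8.1% | 9.5% |

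With the woman as cluster, the rate was 4.6% to 5.4% in all 15 cells.

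**The case against.** The best case against acting is that little depends on it. These endpoints are supportive, need not show non-inferiority, and sit among more than 20 secondary endpoints with no multiplicity adjustment. No decision rule uses their 5% level. In the central example of step 4 the half-width moves by 0.4 points. The pregnancy-rate endpoints cover the same sequence of outcomes per woman with a valid standard error. The correlation comes from biological reasoning, not from the documents, and a negative one would make the planned intervals too wide. Single transfer is the rule under 35 when a good-quality embryo exists, so f = 0.7 is at the high end; the stratified calculations peak at 9.4% to 9.5%, not 9.9%. Finally, analysing in a similar manner does not strictly fix the variance, and the SAP limits intervals and p-values to where they are appropriate.

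Most of this stands as a limit on size. It does not remove the point. The lack of multiplicity adjustment does not make a wrong standard error right. No other variance is given, so a programmer following the SAP would use the binomial one. The SAP's caveat on implantation rate concerns the restriction to women with a transfer, which is a different problem, and it is not repeated for ongoing implantation rate.

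**Conclusion.** The concern holds, conditional on positive within-woman correlation. As written, both implantation endpoints get a standard error that ignores the pairing of embryos. Over the assumed ranges of f and ρ it is about 2% to 16% too small, and a nominal 5% test runs at roughly 5.5% to just under 10%. Moderate values (f of about 0.3 to 0.5, ρ = 0.3) give about 7%. The effect is modest because a woman contributes at most two embryos, and it is largest in the two older strata. The algebra is certain; the size rests on assumed f and ρ. The non-inferiority conclusion and the sample size do not change. It is worth correcting because the endpoints are offered as support for the primary result and the correction is simple.

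**What to change.** Add one or two sentences to SAP 9.3 covering both implantation endpoints:

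- Keep the embryo-level risk difference and the Mantel-Haenszel age weights, and state that n in the weights counts embryos.
- In each arm and age stratum, replace p(1−p)/n with the woman-clustered variance. With x_j the sacs (or viable fetuses) and m_j the embryos transferred for woman j, use p = Σx_j/Σm_j and Var = Σ(x_j − p·m_j)²/(Σm_j)².

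With single transfers only and at most one sac or fetus per embryo, this reduces to the planned formula. It also copes if a woman has more sacs or fetuses than embryos transferred, which the SAP's triplet and higher-order categories allow for.

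Other cluster-valid methods would serve, such as a bootstrap that resamples women or generalised estimating equations with the woman as cluster. Within a stratum, the latter give the same risk difference only with an identity link, an independence working correlation and a robust standard error.

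The cost is a few lines of code, with no new data, subjects or procedures. Intervals widen slightly if the correlation is positive and are essentially unchanged if it is zero.
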